8.6 Follow-up of subjects withdrawn from treatment

Subjects who withdraw from treatment will be followed according to regular medical care.

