8. METHODS

8.1 Study parameters/endpoints

8.1.1 Main study parameter/endpoint

The primary objective of this study is the gathering of data on blood pressure management as a basis for power analysis in future trials. This will be evaluated by a before-after-comparison of systolic and diastolic blood pressure in mmHg as measured by the self-measurements with the Stroke Box.

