8.4 Withdrawal of individual subjects

Subjects can leave the study at any time for any reason if they wish to do so without any consequences. The investigator can decide to withdraw a subject from the study for urgent medical reasons.

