8.5 Replacement of individual subjects after withdrawal

If a subject decides to withdraw from the study, they will not be replaced.

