11.6 Incentives (if applicable)

All devices will be provided by the LUMC. Patients do not have to pay for the devices. Patients are allowed to keep their devices after the study is finished. This is the same for patients who withdraw from the study.

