12. ADMINISTRATIVE ASPECTS, MONITORING AND PUBLICATION

12.1 Handling and storage of data and documents

Routine health care data will be accessible through the electronic patient system of the GP where the patient is registered. After approval, all necessary patient study data will be collected in a coded database. The key to which is available at the research coordinator [name]. Only investigators are authorized to look into the data. A key file will be made, to be able to trace back each individual patient. Both files will be password protected and the password for both files will be changed every three months. No mobile data carriers (i.e. USB-drive, DVD) will be used for that purpose.

Data Collection Forms, Case Report Forms, Informed Consent Forms and all other study documentation containing subject information will be stored under locked conditions when not in use. Computers and all storage devices containing study data will be password-protected. Data stored on the computer will use an alphanumeric code to identify the subject. Access to data is restricted to study personnel and when required the REC or other regulatory bodies as required by law. Essential trial documents and data, as well as a data back-up, will be retained for at least fifteen years. The data back-up will be stored on the network drive of the principal investigator, within the LUMC. To access this network drive, it is required to know the investigator's password, which is changed every three months. Also, it is required to know the passwords to the anonymized database as well as the key file, which are also changed every three months.

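### No blood pressure is planned after a patient stops using the Box, so the before-after change meant for the future trial's sample size may rest on completers or on early last readings

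*Combined protocol and SAP*

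**What the plan says.** Section 8.4 allows exit without conditions: "Subjects can leave the study at any time for any reason if they wish to do so without any consequences". It adds a second route: "The investigator can decide to withdraw a subject from the study for urgent medical reasons". Section 8.5 rules out replacement: "If a subject decides to withdraw from the study, they will not be replaced". Section 8.6 is the whole plan for what follows: "Subjects who withdraw from treatment will be followed according to regular medical care". Sections 8.4 and 8.5 speak of the study and 8.6 of treatment. None of them says whether a patient who merely stops measuring has left the study.

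The main endpoint in section 8.1.1 is blood pressure change: "This will be evaluated by a before-after-comparison of systolic and diastolic blood pressure in mmHg as measured by the self-measurements with the Stroke Box". No window is set for the before or the after value. Under section 8.3 blood pressure is self-measured weekly, and sections 5.1 and 8.3 have the readings uploaded automatically. Section 10.1 will describe the dropout rate and the change in mmHg and use them for the sample size of future trials. It names no analysis set and no missing-data rule.

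Two provisions elsewhere bear on this. Section 11.6 says of the devices: "Patients are allowed to keep their devices after the study is finished", and then: "This is the same for patients who withdraw from the study". Section 12.1 says: "Routine health care data will be accessible through the electronic patient system of the GP where the patient is registered".

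**The concern.** A six-month change needs a blood pressure at about six months. As written, a patient who stops in week 5 returns to usual care and nobody asks for that value. The summary must then leave the patient out or use a reading taken long before month 6. Either choice alters what the reported change means.

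Loss may well be related to outcome. Section 1 warns that stroke-related disability may make it harder for patients to take up self-monitoring, and section 8.4 lets the investigator remove patients on urgent medical grounds. Those who stop could differ from those who continue in both course and blood pressure.

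Estimating blood pressure change for a later trial is the pilot's primary purpose, so any selection carries straight into that use. Reporting the dropout rate shows that loss occurred but does not correct the estimate. The loss is also partly avoidable, since the patient still has the cuff.

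**Working it through.** **1. The plan's own figure.** Section 4.4 expects a blood pressure change in 37.5% of 55 patients and states 20. Check: 0.375 × 55 = 20.6, which agrees after rounding down. The figure uses all 55 patients, with no allowance for loss, and section 4.4 calls 55 the minimum size.

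**2. Inputs that the documents do not give.** There is no dropout rate, SD or mean change. The following are assumptions: loss of 10, 20 or 30%; a gap of 5 or 10 mmHg between the mean changes of completers and leavers; and, for step 4, a within-group SD of 15 mmHg (range 12 to 18). In whole patients, 50, 44 or 38 remain and 5, 11 or 17 are missing.

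**3. Error in the mean change if leavers are omitted.** Error = (missing / 55) × gap.

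| Assumed loss | Missing | Gap 5 mmHg | Gap 10 mmHg |
|---|---|---|---|
| 10% | 5 | 5/55 × 5 = 0.45 | 5/55 × 10 = 0.91 |
| 20% | 11 | 11/55 × 5 = 1.00 | 11/55 × 10 = 2.00 |
| 30% | 17 | 17/55 × 5 = 1.55 | 17/55 × 10 = 3.09 |

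The range is about 0.5 to 3 mmHg. The sign depends on whether leavers change less or more than completers, which is unknown.

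If last readings are used instead, the same formula applies. The gap is then the difference between a stopper's change at the last reading and that patient's change at month 6.

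**4. Error in the variance at 20% loss and a 10 mmHg gap.** All-patient variance = SD² + 0.2 × 0.8 × 10².
- SD 15: 225 + 16 = 241. Completers show 225, and 225/241 = 0.934, about 7% too low.
- SD 12: 144/160 = 0.900, 10% too low.
- SD 18: 324/340 = 0.953, about 5% too low.

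This assumes the same SD in both groups.

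**5. Effect on the share with a change.** Suppose 37.5% of those observed change, and either none or all of the missing do. The half-width is 1.96 × √(0.375 × 0.625 / n).

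| n observed | Expected with a change | 95% half-width, points | All-patient share, lowest to highest |
|---|---|---|---|
| 55 | 20.6 | 12.8 | 37.5% |
| 50 | 18.75 | 13.4 | 18.75/55 = 34.1% to 23.75/55 = 43.2% |
| 44 | 16.5 | 14.3 | 16.5/55 = 30.0% to 27.5/55 = 50.0% |
| 38 | 14.25 | 15.4 | 14.25/55 = 25.9% to 31.25/55 = 56.8% |

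Precision falls only modestly. The wider uncertainty comes from not knowing who left.

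**The case against.** **The analysis is not stated to be completers-only.** A reader might infer that everyone who stops early drops out of the endpoint. The documents do not say so. Weekly readings before stopping are already at the centre, section 8.1.1 sets no month-6 window and section 10.1 names no analysis set. A first-to-last comparison in everyone is equally compatible with the text. This objection stands and limits the point to what may happen. It does not remove the gap, because a last reading in week 5 is not a six-month outcome.

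**The direction of bias is not established.** A reader might infer that completers will show a larger and less variable change. Section 1 says only that disability may reduce adaptation. Sections 4.2 and 4.3 narrow the population to patients going directly home who can use a smartphone, and exclude severe aphasia and incapacity. This stands.

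**No sample-size multiplier follows.** A reader might scale the future sample size by SD² over the squared mean change. With completers at −10 mmHg and SD 15, 10% loss and a 5 mmHg gap give (227.25/9.5²)/(225/10²) = 1.12. With 30% loss and a 10 mmHg gap, (246/7²)/(225/10²) = 2.23. The spread comes entirely from assumed inputs. A randomised trial is also normally sized on a between-group difference, which a single-arm change does not supply. No such factor should be quoted.

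**The remedy is partial.** Patients who stop because they cannot manage the cuff may not provide another reading, and one reading is not a weekly series. Section 1 itself regards practice readings as less accurate than home readings. The consent form was not available for review, so it may already cover data collection after stopping. These points stand and shape the fix.

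**The pilot is descriptive.** It has one arm, tests no hypothesis and will report dropout. That limits the seriousness, but the change in mmHg is still meant to be used.

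**Conclusion.** The point holds in limited form. Stopping the Box and leaving the study are not distinguished, no blood pressure is planned after stopping, and the analysis section does not say how such patients enter the before-after change. The estimate passed to the future trial may therefore describe completers, or mix six-month changes with shorter ones.

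The error of about 0.5 to 3 mmHg in the mean and the roughly 7% understatement of variance illustrate scale only. They rest on the assumed loss, gap and SD, and with no gap both would be zero. The importance is moderate. It is worth correcting because the remedy is cheap and uses a device that the patient already holds.

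**What to change.** 1. **Sections 8.4 and 8.6:** distinguish a patient who stops using the Box from one who withdraws consent for data. Check that the consent form covers this distinction, and amend it only if it does not.
2. **Patients who stop but keep consent:** retain every reading uploaded so far and ask for a month-6 self-measured blood pressure on the cuff they keep.
3. **All patients, completers included, subject to consent:** take the GP-recorded blood pressure nearest month 6. Report it in a separate row as a check, not pooled with self-measurements.
4. **Section 10.1:** report the change for completers and for all patients with a month-6 self-measured value, with the number in each. Define the before and month-6 windows. State how patients without a month-6 value are handled; if last readings are shown, give the week in which they were taken.

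**Cost:** wording in three sections, possibly a sentence in the consent form, and one reminder and one record extraction per patient. Some who stop will decline or be unable to measure, so the gap will shrink but not close.

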8.7 Premature termination of the study

Not applicable.

9. SAFETY REPORTING

9.1 Temporary halt for reasons of subject safety

In accordance to section 10, subsection 4, of the WMO, the sponsor will suspend the study if there is sufficient ground that continuation of the study will jeopardise subject health or safety. The sponsor will notify the accredited METC without undue delay of a temporary halt including the reason for such an action. The study will be suspended pending a further positive decision by the accredited METC. The investigator will take care that all subjects are kept informed.

9.2 AEs, SAEs and SUSARs

9.2.1 Adverse events (AEs)

Adverse events are defined as any undesirable experience occurring to a subject during the study, whether or not considered related to the investigational product. All adverse events reported spontaneously by the subject or observed by the investigator or his staff will be recorded.

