3. STUDY DESIGN

In this pilot study we will evaluate the technical feasibility and clinical implementation of the Stroke Box in a small prospective cohort. After providing the Stroke Box to the patients, detailed information will be provided on the use of the Stroke Box and the patient will be helped with their first use.

The patient will use the Stroke Box to take at-home measurements for six months. Here we will be gathering data on blood pressure management, cardiac rhythm, patient engagement and have a user-based evaluation of the eHealth infrastructure. Patients will perform regular home measurements which the GP can use at the regular visits, and a nurse specialist in the LUMC will assess ECG measurements. We will keep close contact with both patient and GP to help in case of any questions. The patients will have access to the LUMC Box Support helpdesk who are an established customer service desk to help with any Box-related issues. We will ask the patients and GPs to contact us in case of any questions they might have. At the end of the pilot the user evaluation will be done through a questionnaire.

During the regular GP visits after the stroke related hospital admission, the GP and the nurse specialist will have insight in the collected data. We will evaluate the GP's experience of the data insight and technical usability using a questionnaire.

The study is estimated to take 12 months where we will have 6 months of inclusions and 6 months of follow-up.

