8.3 Study procedures

For the small prospective cohort for the pilot, patients who are admitted for an ischemic or hemorrhagic stroke in the LUMC will be included in the day or days before dehospitalization and after post-stroke stabilization. After inclusion we will personally contact the GP of the patient to also ask their willingness to collaborate in the pilot. After agreement of their GP, the included patients will receive the Stroke Box with all devices listed under section 6 of this protocol. Patients will be instructed on usage of the devices by a neurology PhD student. Furthermore, for each device a detailed user guide is available on <https://hartlongcentrum.nl/informatie-voor-patienten/the-box/handleidingen/>.

If extra help is necessary, patients will have an e-consult in which a patient does not have to go to the hospital. Instead, he or she will talk with a specialist from the Box-helpdesk who will be able to guide the patient through the self-measurements and provide technical assistance where necessary.

Patients will be asked to measure their weight and blood pressure once a week where they are recommended to do this on the same day and time every week. Additionally, they will be asked to keep track of their activity data (i.e. steps) on a regular basis, which can be monitored continuously by wearing the smartwatch. All

data will be automatically transferred to the LUMC. In order to code the data, patients will receive an anonymous email address, as described earlier in this protocol. Data will be stored on LUMC-owned servers.

The patient's blood pressure measurements and lifestyle data (measured weight and activity) is accessible for the GP through Medical Dashboard. For GPs who do not yet work with Medical Dashboard, the patient will be asked to show his measurements to the GP in the following way during the regular visits. The patient can either show his measurements in the app or make a printout of the data to be shown to the GP or GP nurse.

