Finally, the first ten patients with a modified Rankin Scale (mRS) ≥ 2 will receive access to the IkOefenZelf platform and will be asked to perform the practice modules on a regular basis.

Patients who smoke will also be asked to install the StopAdvisor app. This app will help them to quit smoking. The app is freely available from the IOS App Store and the Google Play Store.

Questionnaires

At the start and end of the study the patient will receive several questionnaires to evaluate their experiences with self-management, physical activity, healthy lifestyle intentions, their user experience, and their experience with eHealth. To evaluate the change in physical activity and lifestyle of the patient, they will be asked to fill out the SQUASH and HLI questionnaires at the start and end of the study. These questionnaires investigate respectively the amount of physical activity (e.g. sports) a patient has and what their intentions to a healthy lifestyle are (which includes questions on e.g. diet, smoking and alcohol use). In order to evaluate the experience of the patient with the self-management, they will be asked to fill out the PIH questionnaire at the start and the end of the pilot which measures how the patient manages his/her own disease. Finally, to evaluate the patient experience with the overall implementation of the Stroke Box, we will ask them to fill out the MAUQ questionnaire at the end of the study which includes questions on the technical ease-of-use, the general appearance and usefulness of the Stroke Box.

Moreover, we will evaluate the GP experience with the Stroke Box via the AIM, IAM and FIM²⁵ questionnaires for healthcare professionals which are four-item measures of implementation outcomes that are often considered “leading indicators” of implementation success.²⁶ An overview of the questionnaires used is given in the Table below.

Implementation will be assessed by the Reach Efficacy Adoption Implementation Maintenance (RE-AIM) model with a mixed model evaluation based on the normalization process theory.²¹⁻²³ The implementation will be evaluated from the perspective of the neurologists, GPs, practice assistant GP and patients.

Subject	Questionnaire	Estimated time
Physical activity	Short Questionnaire to Assess Health enhancing physical activity questionnaire (SQUASH) ²⁰	5 min
Healthy lifestyle intentions	Healthy lifestyle intentions questionnaire	4 min

Self-management	Partners In Health (PIH) questionnaire ¹⁸	4 min

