10. STATISTICAL ANALYSIS

10.1 Primary study parameter(s)

We will use descriptive statistics to assess blood pressure management, patient engagement and user-based evaluation of the eHealth infrastructure. We will analyze their self-measurement frequency of blood pressure, heart rhythm, weight, and activity using the mean measurements per week. The dropout rate will be described and the change in blood pressure in mmHg. This will be used as a basis for sample size calculation for future trials.

Moreover, we will use descriptive statistics to assess the clinical characteristics of our sample population.

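### Adverse events are captured passively and no study contact is timed to ask about them, so a death or an admission outside the LUMC could be missed or appear only as a dropout

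*Combined protocol and SAP*

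**What the plan says.** Section 9.2.1 sets the capture rule: "All adverse events reported spontaneously by the subject or observed by the investigator or his staff will be recorded". Follow-up takes place at home: "The patient will use the Stroke Box to take at-home measurements for six months" (section 3).

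Section 8.3 describes the contacts in that period. Patients are instructed on the devices at inclusion, after which weekly measurements upload automatically. Technical help is on demand: "If extra help is necessary, patients will have an e-consult in which a patient does not have to go to the hospital". Patients call the nurse specialist after certain watch results. The timed questionnaires come only at the two ends: "At the start and end of the study the patient will receive several questionnaires". Their named topics are physical activity, lifestyle intentions, self-management and app usability.

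Section 3 adds "We will keep close contact with both patient and GP to help in case of any questions" and "We will ask the patients and GPs to contact us in case of any questions they might have". Visits during follow-up are the GP's regular visits. Section 6.4 says in passing that patients are asked about their general health at regular times. Section 12.1 says: "Routine health care data will be accessible through the electronic patient system of the GP where the patient is registered".

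Under section 8.6, patients who withdraw return to regular care. Section 10.1 says: "The dropout rate will be described and the change in blood pressure in mmHg", and these results feed the future sample size.

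**The concern.** Passive capture works when staff meet patients often enough to notice events. Here patients are at home for six months, regular care is with the GP, and the timed study contacts are at the start and the end. The protocol's introduction expects many participants to have physical or cognitive disability after their stroke. Those most likely to have an event may therefore be least able to report it, and a patient who dies cannot report at all.

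Two outputs are at stake. The first is the count of serious adverse events. It goes to the ethics committee each year under section 12.4, and the reporting timeline in section 9.2.2 for fatal or life-threatening events starts only when the study learns of the event. The risk that section 11.4 calls major, a false sense of safety that delays seeking care, would show up as late or serious presentations, which this method could miss. The second is the dropout rate. In a feasibility pilot, losing a patient to a clinical event and losing one who could not or would not use the technology lead to different decisions about the next trial.

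**Working it through.** The plan gives no event rate and no expected dropout, so it has no figure of its own to reproduce. The check has two steps.

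**Step 1. Could any described route bring a death or outside admission to the study's notice?**

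| Route | Where | Timed? | Purpose includes events or vital status? |
|---|---|---|---|
| Spontaneous report or staff observation | 9.2.1 | No | Yes, but passive |
| Study contact with patient and GP | 3 | No | No, tied to questions |
| Helpdesk e-consult | 8.3 | No, on demand | No, technical help |
| Nurse specialist call | 6.4, 8.3 | No, patient starts it | No, watch results |
| Patient questionnaires | 8.3 | Start and end | Not among the named topics |
| General health questions | 6.4 | Said to be regular; no interval, form or owner; absent from 8.3 | Not stated |
| In-app illness questionnaires | 5.1, 6.1 | Time points not given | Not stated |
| GP record | 12.1 | No | Accessible, but not named as a source of either |

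No row combines a stated time during follow-up with the purpose of asking about events. No section says what happens when uploads stop, and none asks the GP to report deaths or admissions. A readmission to the LUMC itself is different, because staff there could see it. The gap therefore concerns deaths and admissions elsewhere.

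**Step 2. Scale, for illustration.**

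Inputs: n = 55 (section 4.4), and p = six-month risk of a death or an admission outside the LUMC. The value of p is an assumption, and patients are taken as independent.

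Expected patients = 55 × p. Chance of at least one = 1 − (1 − p)^55.

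- p = 1%: 55 × 0.01 = 0.55 expected; 1 − 0.99^55 = 42%.
- p = 2%: 55 × 0.02 = 1.1 expected; 1 − 0.98^55 = 67%.
- p = 5%: 55 × 0.05 = 2.75 expected; 1 − 0.95^55 = 94%.

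These are chances that an event occurs, not that it is missed. The documents do not allow the proportion missed to be estimated.

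Each such patient who appears only as a dropout is 1/55 = 1.8 percentage points of the dropout rate.

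**The case against.** The strongest reply is that the study is not out of touch with its patients. It promises contact with patient and GP. Section 6.4 mentions regular health questions, and the app can present questionnaires. Physicians and nurses can look at uploads in the medical record, the nurse specialist hears about watch alerts, and the GP record is accessible. The devices are CE-marked and non-invasive, the study is rated negligible risk in section 12.2, and the pilot is single-arm and descriptive. For inflating a future sample size, loss from all causes is normally the rate that is needed, so a combined figure remains usable.

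Much of this stands, and it rules out several stronger readings that a reader might infer.

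- *Staff have almost no chance of seeing an event.* Not supported: LUMC readmissions, nurse calls, helpdesk contacts and the end-of-study contact could all reveal one.
- *Serious adverse events will be under-counted.* The documents show that this is possible, not that it will happen.
- *Section 10.1 would code these patients as dropouts, or as technology failures.* Section 10.1 neither defines dropout nor has such categories, and section 8.4 separately recognises withdrawal for urgent medical reasons. A patient who has an event and resumes measuring is not a dropout.
- *No questionnaire asks about events.* The documents list instruments and topics, not items.
- *The total dropout rate would be wrong.* A patient who dies is lost under any all-cause definition. What becomes unclear is the reason for the loss.

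The reply does not supply a time, a form or a responsible person for asking about events. Access to the GP record shows that a check is feasible, not that one is planned.

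**Conclusion.** The point holds as a gap in ascertainment. Following the plan as written could miss a death or an outside admission, or leave it visible only as a dropout. The serious adverse event count could then be too low, and the dropout rate could mix clinical events with problems using the technology.

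The size cannot be fixed from the documents. Under an assumed 1% to 5% six-month risk, at least one such event in 55 patients has a chance of 42% to 94%, so the situation is worth planning for. Each patient accounts for 1.8 percentage points of dropout whose cause may be unknown. No sample size or power figure in the protocol changes. The change is worth making because it is cheap and uses records that the protocol already describes as accessible.

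**What to change.** In section 9.2.1, keep spontaneous reports and add:

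1. a fixed item at the end-of-study questionnaire on hospital admissions, new stroke or TIA, and falls;
2. one check at month 6 of the LUMC medical record and the GP record, for events and vital status, in every patient, including those who stopped uploading;
3. a request to each GP, made when the GP agrees to take part, to report deaths and admissions to the study.

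Reconcile section 6.4 with section 8.3: either give the general health questions an interval, a form and a responsible person in 8.3, or remove the statement.

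In section 10.1, define dropout and report it overall and by cause: death or clinical event, technology-related, other. The overall rate still serves for sample-size inflation, and the split serves the feasibility conclusions.

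Cost: a few protocol sentences, one questionnaire item, and about 10 minutes of record review per patient (an estimate), or 55 × 10 = 550 minutes, a little over nine hours in total. The consent text should cover this use of the records. The stated number of serious adverse events may be higher as a result.
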